Patients lost to follow-up before experiencing EDA will be considered as not having had the event. A sensitivity analysis with the maximum bias assumption will be conducted by considering missing data (discontinuation of follow-up before the end of the 2-year follow-up with NEDA) in the interventional arm as failures (non-responders = EDA) and those in the control arm as successes (responders = NEDA).

The rate of EDA in both arms will be estimated and then compared between the two treatment arms using mixed-effects logistic regression (random center effect). The treatment arm will be the factor of interest in the model. Adjustment will be made for randomization stratification factors (center, contrast enhancement on diagnostic brain and spinal cord MRI), known prognostic factors listed in section 4.1.4 of the protocol (Age, Gender, Presence of contrast enhancement on the reference MRI, Lesion load in FLAIR in mm³, Number of lesions with contrast enhancement on the reference MRI, EDSS score at baseline), and the time between CIS and the first administration of the treatment, which varies among patients (from a few days to 95 days = maximum of 90 days between CIS and the reference MRI and the first administration of the study treatment, which takes place on the first Saturday post-MRI). Adjustment for the center effect will be performed by considering the center as a random effect in the model (Kahan 2014, Kahan et al. 2015, Edgar et al. 2021).

The number of lesions with contrast enhancement on the reference MRI could not be determined quantitatively. This information is provided by recording the presence of contrast enhancement with a precision level in 3 modalities (similar to the diagnostic MRI): no lesions with contrast enhancement, one lesion with contrast enhancement, and at least two lesions with contrast enhancement. This information will be used as an adjusting variable only if it is not significantly associated with contrast enhancement on the diagnostic MRI (a randomization stratification factor), for which an adjustment is performed. The statistical significance of the association will be assessed using the Chi-square test or Fisher's exact test if the Chi-square test is not applicable, with a significance level set at < 0.05.

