 - Treatment arm (explanatory variable of interest)
 - Center as a random effect (multiple patients per center)
 - Patient as a random effect (multiple measurements per patient)
 - Visit (temporal chronological variable)
 - Interaction between the treatment arm and the presence of a relapse during follow-

up

- A second mixed-effects regression model will be used to compare the M24 scores of the outcome measures while adjusting for baseline scores (M0):
 - M24 score (outcome variables)
 - Treatment arm (explanatory variable of interest)
 - Center as a random effect (multiple patients per center)
 - M0 score (adjustment variable)

- Interaction between the treatment arm and the presence of a relapse during follow-up

Secondary Objective F: Evaluate treatment tolerance on:

a. The occurrence of AEs and SAEs

- b. Pharmacological measurement of serum concentrations of 25(OH)D2 and 25(OH)D3
- c. Measurement of serum calcium, urinary calcium, and renal function

The number of AEs and SAEs per patient will be described by arm.

For points b and c, a mixed-effects regression model will be used to compare the evolution of measurements during follow-up. The model variables will include:

- Measurements at different visits (outcome variable)
- Treatment arm (explanatory variable of interest)
- Center as a random effect (multiple patients per center)
- Patient as a random effect (multiple measurements per patient)
- Visit (temporal chronological variable)

Secondary Objective G: Initial formulation: Correlate the variation in clinical and imaging parameters with the initial level and changes in the levels of 25(OH)D2 and 25(OH)D3 under treatment.

Reformulated Objective G1: Study the link between the severity of impairment (parameters measured by the baseline MRI, such as the number of lesions, EDSS score) and the vitamin D level measured during pre-screening (25(OH)D2 and 25(OH)D3).

A mixed-effects regression model will be estimated. The model variables will include: - Severity of impairment at inclusion (outcome variable). Several variables will be successively modeled: binary variables for MRI parameters (using a logistic regression model) and a quantitative variable for the EDSS score.

- Levels of 25(OH)D2 and 25(OH)D3 at pre-inclusion (explanatory variables of interest)
- Treatment arm (adjustment variable)
- Center as a random effect (multiple patients per center)

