Reformulated Objective G2: Study the link between the occurence of EDA and vitamin D levels (25(OH)D2 and 25(OH)D3) during follow-up.

A mixed-effects regression model will be estimated. The model variables will include:

- Occurrence of EDA (relapse or MRI) (outcome variable)
- Treatment arm (adjustment variable)
- Center as a random effect (multiple patients per center)

- Patient as a random effect (multiple measurements per patient)

- Levels of 25(OH)D2 and 25(OH)D3 measured during follow-up (explanatory variables of interest)

- Visit (temporal chronological variable)

Objectives H, I, and J do not require statistical analyses and involve the establishment of biobanks.

Secondary Objective K: Estimate the discordance rate between the presence of NEL on follow-up MRI scans determined by the neurologist during the study and the result of the centralized MRI analysis performed at the end of the study (EDA not confirmed retrospectively or, conversely, detection of EDA not identified during the study). Additionally, estimate the rate of patients retrospectively identified as erroneously included based on centralized MRI reevaluation (inclusion criterion MRI not verified during centralized reading of the baseline MRI).

Discordance between decisions made during the study by neurologists and the results of centralized reevaluation analyses will be determined for each patient throughout his followup. The discordance rate will be estimated and presented with a 95% confidence interval.

The rate of patients retrospectively identified as erroneously included will also be estimated and presented with a 95% confidence interval.

Anticipated Level of Significance:

A difference will be considered statistically significant when the significance level of the test is less than or equal to 0.05.

Method for Handling Missing, Unused, or Invalid Data:

For the analysis of the primary outcome, if a patient is lost to follow-up without experiencing EDA, they will be considered as NEDA at the end of the 2-year follow-up and censored at the date of the last known status.

Regarding the adjustment variables in the primary analysis:

- If the gadolinium-enhancement status at the diagnostic MRI scan is unknown for a given patient, the missing data will be imputed by the gadolinium-enhancement status at the

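### Objectives G1 and G2 are observational level–outcome associations, but their models omit the patient-level covariates needed to limit confounding

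*SAP*

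**What the plan says.** Under Secondary Objective G, the SAP splits an initial correlation objective into two parts, each with its own list of model terms.

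- **G1.** The aim is to "Study the link between the severity of impairment (parameters measured by the baseline MRI, such as the number of lesions, EDSS score") in relation to the vitamin D level at pre-screening. The outcome is "Severity of impairment at inclusion (outcome variable"), the exposures are "Levels of 25(OH)D2 and 25(OH)D3 at pre-inclusion (explanatory variables of interest"), the only fixed adjustment is "Treatment arm (adjustment variable"), and the remaining term is "Center as a random effect (multiple patients per center").
- **G2.** The aim is to "Study the link between the occurence of EDA and vitamin D levels (25(OH)D2 and 25(OH)D3) during follow-up". The exposures are "Levels of 25(OH)D2 and 25(OH)D3 measured during follow-up (explanatory variables of interest"). The other terms are treatment arm (again as an adjustment variable), visit, and random effects for centre and patient.

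Primary Analysis (Rate of EDA) adjusts for the stratification factors, for "known prognostic factors listed in section 4.1.4 of the protocol (Age, Gender, Presence of contrast enhancement on the reference MRI", lesion load, number of enhancing lesions and baseline EDSS), and for the time from CIS to first administration. The SAP then replaces lesion volume by a two-category T2/FLAIR lesion count. Primary Analysis (Time to EDA) states that the same variables are used in the Cox model. Objective G has no such statement.

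**The concern.** Vitamin D level is not randomised in G1, and only partly so in G2. A patient characteristic that affects both level and outcome can therefore produce an association with no causal link behind it. Covariate adjustment is the ordinary defence. The SAP applies it to the randomised comparison, which needs it least for bias, and not to these two analyses, which need it more.

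The section Anticipated Level of Significance sets one 0.05 threshold for all tests, and neither G1 nor G2 is labelled observational or exploratory. A significant level–severity or level–EDA coefficient from a cholecalciferol trial could be set beside the randomised result and read as supporting or weakening it, when it might reflect age, gender or baseline disease activity.

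**Working it through.** The SAP gives no sample size, effect or power for Objective G, so there is no figure to reproduce.

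**1. Term lists side by side**

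| Term | Primary model | G1 | G2 |
|---|---|---|---|
| Treatment arm | factor of interest | adjustment | adjustment |
| Centre (random) | yes | yes | yes |
| Patient (random) | no | no | yes |
| Visit | no | no | yes |
| Age, gender | yes | no | no |
| Contrast enhancement | yes | no | no |
| T2/FLAIR lesion category | yes | not as a covariate | no |
| Baseline EDSS | yes | outcome | no |
| Time from CIS to first dose | yes | no | no |

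**2. What arm does in G1.** Level is measured at pre-screening and severity at inclusion or on the baseline MRI, and the first dose follows that MRI. Arm is assigned at random and cannot have influenced either quantity, so it is not a common cause of them. Including it neither biases the level coefficient nor removes confounding.

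**3. What arm does in G2.** With arm in a linear model, the level coefficient uses only the part of level left after regression on arm (Frisch–Waugh). In a numerical check, the between-arm difference in residual level was 1.6e-16, that is, zero. For a 1:1 trial with an arm shift of s within-arm SDs, the share of level variance due to arm is (s²/4)/(1 + s²/4):

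- s = 1: 0.25/1.25 = 20%
- s = 2: 1/2 = 50%
- s = 3: 2.25/3.25 = 69%

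The SAP gives no value for s. One qualification applies: arm and visit enter additively, so an arm-by-visit difference in level is not removed. Hence the coefficient rests *mainly* on within-arm variation.

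**4. Illustrative size, by formula.** Assume one omitted factor with correlation ρ to both level and outcome, no true link, 316 patients (the denominator given with the lesion-load data) and a two-sided 0.05 test (the SAP does not state sidedness).

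- Apparent correlation r = ρ²: 0.2² = 0.04; 0.3² = 0.09.
- z = r√316: 0.04 × 17.78 = 0.71; 0.09 × 17.78 = 1.60.
- Rejection probability P(|Z + z| > 1.96): about 11%; about 36%.

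**5. Illustrative size, by simulation.** Logistic model, n = 316, 1:1, 2,000 replicates, true level effect zero, EDA about 65%, one confounder with log-odds 0.5 per SD, arm shift of 1 or 3 within-arm SDs, one level per patient and no random effects. All of these settings except n are assumptions.

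| Analysis | Confounder–level correlation | Mean level coefficient | False positives |
|---|---|---|---|
| G1 with arm | −0.2 | −0.094 to −0.098 | 14% |
| G1 with arm | −0.4 | −0.188 to −0.192 | 37–38% |
| G2 with arm | −0.2 | −0.094 to −0.096 | 12–13% |
| G2 with arm | −0.4 | −0.189 to −0.194 | 34–35% |
| G1 or G2, confounder added | −0.2 or −0.4 | about 0 | 4–6% |
| G1 or G2, no confounding | 0 | about 0 | 4–5% |

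Dropping arm from G1 left the coefficient unchanged (−0.098 both ways at −0.2; −0.187 against −0.188 at −0.4, shift 1), which confirms step 2.

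**The case against.** The strongest reply is that both objectives set out only to study a link, with no causal claim, and that nothing in them feeds the primary analysis. That stands, and it limits the point to interpretation of a secondary objective.

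Three stronger readings are tempting and are not supported.

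- A reader might infer that the arm term in G1 causes confounding. It does not. It is redundant and costs one degree of freedom; the weakness is what is missing.
- A reader might infer that adjusting for arm in G2 is a mistake because it takes out the randomised contrast. Without arm the simulated bias was indeed smaller (coefficient −0.03 to −0.08 at correlation −0.2). But the randomised comparison is already made in the primary analysis, and whether level relates to EDA beyond assigned arm is a legitimate separate question. Within-arm variation may also include adherence, individual response and change over visits, so it is not just background level.
- A reader might infer that the patient random effect in G2 deals with confounding. A random intercept models repeated measures; it does not remove between-patient confounding.

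It is also fair to object that the SAP mentions neither season nor sampling dates, and nowhere says that age or gender is related to vitamin D level. The case here rests on the SAP's own list of prognostic factors for G2, and on age and gender as plausible common causes for G1. Season is at most an optional addition.

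Finally, the SAP does not say which of the repeated levels in G2 precede EDA. More covariates do not settle that; it is a separate matter.

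**Conclusion.** The point holds as a recommended change. G1 has no fixed adjustment that controls confounding. G2 has arm and visit but none of the baseline factors that the SAP itself treats as prognostic for EDA. Both would be tested at 0.05 as they stand.

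The size of any bias cannot be derived from the SAP. The false-positive rates of 11% to 36% by formula, and 12% to 38% by simulation, rest on assumed correlations and a single omitted factor. They show what could happen, not what to expect. Nor does the SAP support any particular share of level variance explained by arm. The randomised primary result is unaffected.

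**What to change.** - **G1.** Replace treatment arm with age, gender and time from CIS. Do not adjust for the severity measures (baseline MRI parameters, EDSS) that serve as outcomes.
- **G2.** Keep treatment arm, visit and the random effects. Add the primary model's baseline covariates: age, gender, contrast enhancement, T2/FLAIR lesion category, baseline EDSS and time from CIS to first dose.
- **Both.** State that the results are observational associations and do not estimate the effect of treatment. Add month of sampling only if sampling dates are held.
- **Missing covariates.** The SAP's rules for missing CIS date, enhancement status, lesion category and EDSS are written for the primary analysis. Say whether they also apply wherever these covariates are used in Objective G.

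The G2 covariates are already defined for the primary analysis, so the change is mainly wording. The downside is a few degrees of freedom and slightly wider intervals.

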Statistical Analysis Plan

December 21st, 2023

NCT01817166

PHRC-N/2012/ET-01

Efficacy of Cholecalciferol (Vitamin D3) for Delaying the Diagnosis of MS After a Clinically Isolated Syndrome

Final detailed statistical analysis plan drafted before data lock and before the commencement of statistical analyses.

An initial data analysis will provide a description of each arm. Statistical results will be presented using mean and standard deviation for quantitative variables with a Gaussian distribution, and median and interquartile range for other quantitative variables. For qualitative variables, frequencies and associated percentages will be presented.

Demographic, clinical (initial relapse), radiological (diagnostic MRI), and biological (lumbar puncture, vitamin D) data will be described. In particular, it will be determined for each patient whether the diagnostic criteria of McDonald 2017 are met at inclusion (Thompson et al., 2018).

The statistical analysis will be conducted by the BESPIM of the CHU de Nîmes using R 4.1.1 or a later version (R Core Team (2021). R Foundation for Statistical Computing, Vienna, Austria).

Primary Analysis (Rate of EDA)

The primary objective is to assess the efficacy and tolerance over 2 years of treatment with Cholecalciferol (Vitamin D3) in patients who have experienced a clinically isolated syndrome at high risk of multiple sclerosis (CIS, according to the McDonald criteria of 2005). This efficacy will be measured by comparing the risk of conversion to relapsing-remitting multiple sclerosis (RRMS) within 2 years after CIS, according to 2005 McDonald criteria (new lesions on follow-up brain and spinal cord MRIs or new relapses) (McDonald et al., 2001; Polman et al., 2005), between the arm receiving Cholecalciferol and the arm receiving the placebo.

Following the actual diagnostic criteria for MS (McDonald 2017), most patients present with a diagnosis of active MS and conversion corresponds to the current concept of EDA (evidence of disease activity defined by clinical relapses or imaging (gadolinium-enhancing lesions or new or unequivocally enlarging T2/FLAIR lesions) (Lublin et al., 2013) an "no conversion" corresponds to NEDA (no evidence of disease activity). Hence, the event will be the occurrence of EDA within the two years of follow-up (relapse and/or appearance of new or enlarging lesions (NEL) on follow-up MRIs at 3, 12, and 24 months).

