Furthermore, the lesion load in FLAIR in mm³ (reference MRI) is available only for 258 out of 316 patients (those for whom the MRI images could be retrieved). Moreover, obtaining this volume is not reliable because the software does not provide a sufficiently precise estimate. Therefore, no adjustment will be made for the lesion load, and the number of T2/FLAIR lesions on the reference MRI will be used instead as an indicator of lesion load (in 2 modalities: <9 lesions, >= 9 lesions).

In the event of the use of an incorrect stratum during randomization (randomization performed for the stratum with contrast enhancement on the diagnostic MRI while the true value was an absence of contrast enhancement, and vice versa), the analyses will be adjusted for the contrast enhancement value on the diagnostic MRI (Yelland et al., 2022). The stratum error rate will be described by arm.

Primary Analysis (Time to EDA)

Time to EDA is the duration between the date of the first administration of the experimental treatment and the date of EDA.

Date of EDA is:

- The date of the "conversion MRI" for patients with EDA determined by the appearance of NEL on MRI without having a relapse during the follow-up,

- The date of the first symptoms of a relapse for patients with EDA determined by a new relapse without the appearance of NEL on MRI during the follow-up,

- The earlier of the two dates between the date of the first symptoms and the date of the MRI showing NEL for patients who have both a relapse and NEL on MRI during the follow-up.

Patients lost to follow-up or not showing EDA during the follow-up will be right-censored at the date of the last news. The endpoint date will be established for each patient at the date of the end-of-study visit conducted 24 months (2 years) after inclusion.

Time to EDA in both arms will be graphically represented using the Kaplan-Meier method.

The proportional risk of EDA in the experimental arm compared to the placebo arm will be estimated along with its 95% confidence interval using a random-effects Cox model (random center effect) after checking the proportional hazards assumption. Adjustment will be made for the same variables as those used when analyzing the rate of EDA.

Secondary Analyses

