Secondary Objective A: Evaluate clinical efficacy on the number of relapses during the study period. The determination of the number of relapses is based on data from the EDA visit and the summary table of relapses based on the evaluation at Month 24. The number of relapses will be compared between the two arms using a non-parametric Mann-Whitney Wilcoxon test.

Secondary Objective B1: Describe the parameters of magnetic resonance imaging (brain and spinal cord MRI) at the "conversion MRI":

- Appearance of NEL on brain MRI in T2/FLAIR (including size increase) and/or on spinal cord MRI in T2 ("conversion MRI" Yes/No)

- New brain or spinal cord gadolinium-enhancing T1 lesions (active lesion(s) Yes/No)

- Lesion load in mm³ of each brain MRI from the FLAIR sequence

- Total number of gadolinium-enhancing T1 lesions (categorical measure: none, one, at least two)

Secondary Objective B2: Describe the magnetic resonance imaging (brain and spinal cord MRI) parameters during follow-up:

Normalized brain volume obtained from the 3D T1 sequence at different visits
Change in global brain volume (mm3, from the 3D T1 sequence) between the baseline examination and the 2-year examination on one hand, and between the 3-month examination and the 2-year examination on the other hand, to limit the effect of pseudo-atrophy after the first relapse

Secondary Objective C: Evaluate efficacy on disability progression, measured by the EDSS score and Kurtzke functional scores (Kurtzke 1983; Noseworthy et al. 1990; Goodkin et al. 1992) at baseline and during follow-up, then considering scores at M0 and M24 only.

Secondary Objective D: Evaluate efficacy on cognitive abilities (PASAT) (Cutter et al. 1999; Fischer et al. 1999; Parmenter et al. 2006) at baseline and during follow-up, then considering scores at M0 and M24 only.

Secondary Objective E: Evaluate efficacy on quality of life (EQ5D, SF36, TLS-QoL10, and TLS-COPING10 questionnaires), fatigue (FSMC questionnaire), and anxiety/depression (HADS questionnaire) at baseline and during follow-up, then considering scores at M0 and M24 only.

For Objectives C, D, and E:

- A first mixed-effects regression model will be used to compare the evolution of the outcome measures (EDSS score for Objective C, PASAT score for Objective D, and quality of life scores for Objective E). The model variables will include:
 - Scores at different visits (outcome variables)

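### Objective G2 puts a patient random effect and a visit term on EDA without defining EDA by visit or ordering it after the 25(OH)D level

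*SAP*

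**What the plan says.** In Reformulated Objective G2 the outcome is "Occurrence of EDA (relapse or MRI) (outcome variable)". The exposures are "Levels of 25(OH)D2 and 25(OH)D3 measured during follow-up (explanatory variables of interest)". The other terms are arm, visit, a random centre effect and "Patient as a random effect (multiple measurements per patient)". Only the vitamin D levels are described as measured over follow-up.

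The SAP's event definition stands under the primary analysis. Primary Analysis (Rate of EDA) first describes EDA as a concept (relapse, enhancing lesions, or new or enlarging lesions) and then fixes the event: "Hence, the event will be the occurrence of EDA within the two years of follow-up". Primary Analysis (Time to EDA) gives each patient one date. For a patient with both a relapse and NEL it is "The earlier of the two dates between the date of the first symptoms and the date of the MRI showing NEL". Secondary Objective A speaks of a single EDA visit, its count being "based on data from the EDA visit and the summary table of relapses". For patients lost without EDA, the missing-data section says "they will be considered as NEDA at the end of the 2-year follow-up", in a sentence limited to the primary outcome.

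By contrast, the longitudinal models for Objectives C, D, E and F each list scores or measurements at the different visits as the outcome.

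G2 names no link. Reformulated Objective G1 handles "binary variables for MRI parameters (using a logistic regression model)" and the primary analysis of EDA is also logistic, so a logistic link is assumed below.

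**The concern.** A patient random effect needs an outcome that can vary within a patient from visit to visit. G2 uses the same term, occurrence of EDA, that the SAP elsewhere treats as one event per patient, and it gives no rule for turning that event into visit rows. It also does not say which 25(OH)D value goes with which period at risk, so a level sampled after EDA could be used to explain it.

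G2 is the only planned analysis that links 25(OH)D during follow-up to EDA. Two analysts who apply the SAP's own event to the stated model could report different associations from the same data.

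**Working it through.** The SAP gives no event count or power for G2, so there is no figure to reproduce. The check asks whether the stated model can be estimated under each way of laying out the rows.

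**Inputs from the SAP:** 316 patients; follow-up MRI at 3, 12 and 24 months; R 4.1.1 or later.

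**Assumptions not in the SAP:** levels available at those three visits; logistic link; 50-79% of patients with EDA, depending on the run; a true vitamin D coefficient of -0.3 (log hazard ratio per within-arm SD, or log-odds per 30 units) or none; 30 centres with SD 0.3 where centre is modelled.

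**Model:** logit P(Y_ij = 1) = visit_j + b1·arm_i + b2·D3_ij + b3·D2_ij + centre + u_i, with u_i ~ N(0, σ²).

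**Step 1: profile over σ.** One simulated trial, 210 of 316 patients with EDA, one vitamin D level, no centre effect. Entries are log-likelihood, with the vitamin D coefficient per 30 units in brackets.

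| σ | Two-year status copied to each visit | Cumulative status | At-risk rows only | Separate status per visit |
|---|---|---|---|---|
| 0 | -581.1 | | -402.22 (-0.35) | -608.05 (-0.34) |
| 1 | | | -402.52 (-0.43) | -593.11 (-0.37) |
| 2 | | -465.83 (-0.54) | -403.37 (-0.54) | -604.65 (-0.40) |
| 4 | -284.8 | -426.12 (-0.69) | -404.99 (-0.70) | -658.92 (-0.41) |
| 16 | -218.6 | -407.55 (-1.43) | | |
| 32 | -208.1 | -407.33 (-2.70) | | |

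- *Copied status.* Every patient is all 0 or all 1, so the likelihood keeps rising with σ.
- *Cumulative status.* From σ = 16 to 32 the log-likelihood gains 0.22 while the coefficient grows by 2.70/1.43 = 1.9. The data hardly choose σ, but the answer depends on it.
- *At-risk rows.* The profile is almost flat: a loss of 0.30 from σ = 0 to 1.
- *Separate status per visit.* There is a clear maximum near σ = 1 and the coefficient is stable.

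**Step 2: replicates.** 40 per setting, EDA 50-73%, σ capped at 15. Copied and cumulative status reached the cap in 100%. On at-risk rows with true σ = 1, 30-38% of fits collapsed to about 0 and 10-13% reached 10 or more. With a separate status per visit the median was 1.01.

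**Step 3: the model in R 4.3.3.** Six simulated trials, 58-64% EDA.

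- *Copied status:* fitted patient SD 51-56 by Laplace, but 145-150 with 7 quadrature points and 159-338 with 15 (the quadrature fits omit centre). The 22 of 30 fits without a warning all had |z| ≤ 0.43, including those in the three trials with a real link. Those trials gave |z| of 2.6-3.3 on at-risk rows with the previous level.
- *Cumulative status:* three Laplace fits of the same model in one trial gave odds ratios 0.51, 0.93 and 0.86, none with a warning. The largest-to-smallest ratio within a trial was 1.03-3.85 (median 1.5).
- *Incident EDA, all rows kept:* patient SD 0 in 6 of 6. A patient has at most one 1, and a random intercept cannot represent the negative within-patient correlation that follows.
- *Separate status per visit:* SD 0.98-1.40 (simulated 1), with odds ratios equal to three decimals at 7 and 15 points in 6 of 6.

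**Step 4: dilution with incident EDA, all rows kept** (complementary log-log, previous levels, 200 trials per EDA rate, true coefficient -0.30).

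| EDA | Rows after EDA | All rows | Loss | At-risk rows |
|---|---|---|---|---|
| 51% | 19% | -0.25 | 0.05/0.30 = 17% | -0.30 |
| 65% | 26% | -0.22 | 0.08/0.30 = 27% | -0.30 |
| 79% | 34% | -0.19 | 0.11/0.30 = 37% | -0.30 |

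This dilution arises only if 25(OH)D was sampled after EDA, which the SAP does not say.

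**The case against.** The strongest reply is that G2 means a per-visit outcome. The one-event wording and the single date stand under primary-analysis headings, and the NEDA rule for losses is expressly about the primary outcome. The EDA concept could be scored at any visit, MRI is scheduled at three follow-up times, and G2's patient and visit terms repeat the template of Objectives C to F. Read that way, the model works. This stands as a plausible intent. It does not settle the matter, because the SAP states neither the interval, nor how relapses between visits are assigned, nor whether visits after first EDA count, nor which level precedes which interval.

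The largest SDs come from copying the two-year status, which no text instructs, and the quadrature fits omit centre. That is fair. In the same trials odds ratios mostly agreed under copied status, and direction was mostly unchanged under cumulative status. However, in two further simulated trials with cumulative status the odds ratio rose from 0.81 and 0.86 at σ = 0 to 1.33 and 1.93 at σ = 32.

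On at-risk rows the harm is to the size of the estimate. In 24 simulated trials with σ fixed at 0, 1 and 3, the likelihood-ratio verdict at 0.05 was the same in all 24. So under that coding the patient term makes the odds ratio unreliable, but a wrong test was not shown.

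The missing link function is minor, since the SAP uses logistic models for binary outcomes elsewhere.

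**Conclusion.** The point holds as a mismatch between the G2 model and the event the SAP defines. Applied to that event, the patient variance is very large, zero, or barely informed, and the vitamin D coefficient depends on row coding and software. No time order between level and EDA is fixed under any reading.

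Three stronger readings are not supported:

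- *That the G2 model cannot be estimated at all.* It can, if EDA is scored separately at each visit; the SAP simply does not say so.
- *That activity after first EDA was not recorded.* Objective A counts relapses using a Month 24 summary, and Objective K compares NEL readings throughout each patient's follow-up. Whether MRI and 25(OH)D sampling continued after EDA is a protocol matter.
- *That the trial's main result is at risk.* The primary rate and time-to-EDA analyses do not use this model.

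The figures are illustrative and rest on the assumptions listed with the check. G2 is a secondary observational analysis. The text should be corrected before it is run, but the consequence is confined to G2.

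**What to change.** State which outcome G2 means, then use the matching model.

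**First EDA.** Drop the patient random effect. Use the random-centre Cox model already planned for time to EDA, or a discrete-time model on at-risk visits. Adjust for arm and enter 25(OH)D2 and 25(OH)D3 as time-dependent covariates equal to the last value before each risk time. Patients leave the risk set at EDA. In simulation the discrete-time model returned -0.30 at all three EDA rates (95% interval coverage 0.94-0.96) and the Cox model -0.30, -0.29 and -0.29. This shows that the fit is regular but is weak evidence of validity, because the data were generated with prior levels.

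The cost is wording and a new row layout, with no new data. Levels after first EDA go unused, and levels can be months old. Patients with EDA before the first follow-up sample contribute only a pre-treatment level. If 28% of the cumulative hazard falls in the first 3 months, that is 59/(0.51 × 316) = 37%, 84/(0.65 × 316) = 41% and 118/(0.79 × 316) = 47% of EDA cases. This also moves away from G2's stated interest in levels during follow-up.

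**Repeated activity.** Define EDA per visit interval (new relapse or NEL since the previous visit), name the logistic link, keep the mixed model, and use the level measured at or before the start of the interval. This needs relapse and NEL status for intervals after first EDA. Relapses appear to be captured; confirm from the protocol that MRI and 25(OH)D sampling continued.
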